6.3.2 Management of Anemia

Anemia is one of the multiple myeloma-related organ/tissue dysfunction and is generally related to bone marrow infiltration or renal dysfunction. Subject should be monitored for changes in hemoglobin as described in the schedule of assessments (see [Table 5](#)). Increased monitoring should be implemented in subjects whose hemoglobin < 8 g/dL. Subjects should have anemia corrected in accordance with the local practice and institutional guidelines. Hemoglobin parameters of grade 3 but not considered as clinically relevant (ie, without symptoms of anemia and not leading to a clinical intervention including withdrawal of investigational product treatment, transfusion, or significant additional concomitant therapy) will not require discontinuation of AMG 224. However, treatment should be discontinued for persistent (ie, ongoing > 3 weeks after the end of a treatment cycle) grade 3 or 4 anemia in the absence of detectable multiple myeloma which may reflect a prolonged marrow toxic effect of AMG 224.

6.3.3 Management of Infections

Subjects with evidence of existing infection should be closely monitored while being treated with AMG 224. Subjects with active systemic infections requiring IV antibiotics, antivirals, or antifungals should not be dosed with AMG 224 until infection has resolved

and if being treated with an anti-infectious therapy, the course of such therapy should have been completed. Management should be tailored to the appropriate prophylaxis and/or treatment for the underlying infection according to the local standard of care and institutional guidelines.

6.3.4 Management of Peripheral Neuropathy

Peripheral neuropathy is a common side effect of multiple myeloma standard of care therapy. Thorough assessment of baseline peripheral neuropathy is required at screening (see [Appendix H](#)). Subjects should be clinically monitored on ongoing basis for signs and symptoms of peripheral neurotoxicity according to the schedule of assessments (see [Table 5](#)). AMG 224 should be temporarily withheld in subjects experiencing Grade 3 or 4 peripheral neuropathy until resolution to grade 1 or baseline. Peripheral neuropathy should be managed according to the local standard of care and institutional guidelines.

6.3.5 Management of Cardiac Arrhythmia

Subjects with risk factors for, or evidence of, existing heart disease should be closely monitored throughout their treatment with AMG 224. Subjects should be clinically monitored on ongoing basis for cardiac function (blood pressure, heart rate, and ECG) according to the schedule of assessments (see [Table 5](#)). The administration of AMG 224 should be withheld if grade 3 or 4 arrhythmias (including tachycardia) develop or appear to be exacerbated by AMG 224 treatment. Treatment may be resumed once the signs and symptoms resolve to baseline value or grade 1. Management should be tailored to the appropriate treatment for the underlying cardiac disorder according to the local standard of care and institutional guidelines.

6.3.6 Management of Renal Toxicities

Renal dysfunction is one of the multiple myeloma-related organ/tissue dysfunction. Renal function must be monitored closely during treatment with AMG 224. Serum chemistry values, including BUN, serum creatinine, and urine for urinalysis and microscopic exam (microscopic exam only needed for positive dipstick), must be obtained and reviewed prior to each dose of AMG 224 per the schedule of assessments (see [Table 5](#)). AMG 224 must be held for subjects with CrCl or eGFR <30 ml/min/1.73m² or any other grade 3 or 4 renal toxicity any time during study treatment participation. Management should be tailored to the appropriate treatment for the underlying renal disorder according to the local standard of care and institutional guidelines.

Approved

6.4 Hepatotoxicity Stopping and Rechallenge Rules

Subjects with abnormal hepatic laboratory values (eg, alkaline phosphatase [ALP], aspartate aminotransferase [AST], alanine aminotransferase [ALT], total bilirubin [TBIL]) or international normalized ratio [INR]) or signs/symptoms of hepatitis may meet the criteria for withholding of investigational product. Withholding is either permanent or conditional depending upon the clinical circumstances discussed below (as specified in the Guidance for Industry Drug-Induced Liver Injury: Premarketing Clinical Evaluation, July 2009).

6.4.1 Criteria for Permanent Withholding of AMG 224 due to Potential Hepatotoxicity

AMG 224 should be permanently withheld and the subject should be followed according to the recommendations in [Appendix A](#) (Additional Safety Assessment Information) for possible drug-induced liver injury (DILI), if ALL of the criteria below are met:

Increased AST or ALT from the relevant baseline value as specified below:

Baseline AST or ALT value	AST or ALT elevation
< ULN	> 3x ULN

AND

TBIL > 2 x ULN or INR > 1.5

AND

No other cause for the combination of the above laboratory abnormalities is immediately apparent; important alternative causes for elevated AST/ALT and/or elevated TBIL values include, but are not limited to:

- Hepatobiliary tract disease
- Viral hepatitis (eg, Hepatitis A/B/C/D/E, Epstein-Barr Virus, Cytomegalovirus, Herpes Simplex Virus, Varicella, Toxoplasmosis, and Parvovirus)
- Right sided heart failure, hypotension or any cause of hypoxia to the liver causing ischemia
- Exposure to hepatotoxic agents/drugs including herbal and dietary supplements, plants, and mushrooms
- Heritable disorders causing impaired glucuronidation (eg, Gilbert's syndrome, Crigler-Najjar syndrome) and drugs that inhibit bilirubin glucuronidation (eg, indinavir, atazanavir)
- Alpha-one antitrypsin deficiency
- Alcoholic hepatitis

- Autoimmune hepatitis
- Wilson’s disease and hemochromatosis
- Nonalcoholic Steatohepatitis (NASH) or other “fatty liver disease”
- Non-hepatic causes (eg, rhabdomyolysis, hemolysis)

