4.1 Inclusion Criteria

- 101 Subject has provided informed consent prior to initiation of any study-specific activities/procedures.
- 102 Age \geq 18 years old at the time of signing the informed consent.
- 103 Subject must have a pathologically documented, definitively diagnosed, multiple myeloma relapsed or refractory progressive disease after at least 3 lines of therapy for multiple myeloma (see [Appendix D](#) and [Appendix G](#) for further details). Prior therapeutic treatment or regimens must include proteasome inhibitors (eg, bortezomib) and immunomodulatory drugs (eg, lenalidomide).
- a. For group A expansion cohort prior therapy for multiple myeloma must include a CD38 targeting antibody.
 - b. For group B expansion cohort prior therapy for multiple myeloma must not include a CD38 targeting antibody.
- 104 Subject must be willing and able to undergo bone marrow aspirate per protocol (with or without bone marrow biopsy per institutional guidelines).
- 105 Measurable disease per the IMWG response criteria (assessed within 28 days prior to day 1), as indicated by one or more of the following:
- Serum M-protein \geq 1 g/dL
 - Urine M-protein \geq 200 mg/24 hours
 - Subjects who do not meet 1 of the 2 prior criteria: serum Free Light Chain (sFLC) \geq 10 mg/dL (\geq 100 mg/L) and an abnormal sFLC ratio ($<$ 0.26 or $>$ 1.65) as per the IMWG response criteria
- 106 Eastern Cooperative Oncology Group (ECOG) performance status of \leq 2
- 107 Life expectancy of $>$ 3 months, in the opinion of the investigator.
- 108 Hematological function, as follows, without transfusion support:
- Absolute neutrophil count \geq $1.0 \times 10^9/L$,

Approved

- Platelet count $\geq 75 \times 10^9/L$ (in patients with $< 50\%$ of bone marrow nucleated cells were plasma cells) or $\geq 50 \times 10^9/L$ (in patients with $\geq 50\%$ of bone marrow nucleated cells were plasma cells) without transfusion or growth factor support
 - Hemoglobin $> 8 \text{ g/dL}$ ($> 80 \text{ g/L}$)
- 109 Coagulation function, as follows: PT/INR and PTT $< 1.5 \times$ Institutional Upper Limit of Normal (ULN).
- 110 Renal function as follows; estimated Glomerular filtration rate based on MDRD (Modification of Diet in Renal Disease) calculation $> 45 \text{ mL/min/1.73 m}^2$
- 111 Hepatic function, as follows; AST and ALT $< 3 \times$ ULN, Total bilirubin $< 1.5 \times$ ULN (except subjects with Gilbert's syndrome)

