During the DLT-window, if the dosing is delayed for more than 7 days the subject will be removed from the study and will be replaced. After DLT-window, if the dosing is delayed for ≤ 3 weeks, the subject should resume the treatment as soon as possible if deemed safe by the investigator. The investigator should inform the Amgen Clinical team as soon as the unexpected dosing interruption occurs. If the dosing of AMG 224 is delayed more than 3 weeks (missing 1 cycle) due to treatment-related adverse events, the subject will be removed from the study. If the dosing delay occurred under conditions other than those associated with AMG 224 related toxicities, the case will be reviewed by Amgen medical monitor to determine whether the subject will be allowed to resume AMG 224 treatment.

Rules for Withholding or Restarting

AMG 224 should be withheld for any of the following:

- Suspected DLT (including AE that meet DLT definition outside DLT window)
- Grade 3 thrombocytopenia (follow the thrombocytopenia management in [Section 6.3.1](#))
- Aspartate aminotransferase (AST) or alanine aminotransferase (ALT) greater than 3x ULN or total bilirubin greater than 1.5x ULN

AMG 224 dosing can be resumed if the toxicities resolve to grade ≤ 1 or return to subjects' baseline values. The restarting of therapy should be deemed safe by the investigators and Amgen's medical monitor.

Rules for Permanent Discontinuation

Subjects will permanently discontinue from the investigational product if:

- Subjects experience adverse events meeting the DLT criteria at any time. Subjects will be followed until the DLT is resolved, returns to baseline value or is considered stable. Subjects will be withdrawn from AMG 224 treatment and will be treated as deemed appropriate by the investigator or treating physician. Except for:
 - Subjects showing evidence of response or subjects who in the opinion of the investigator may be responding to AMG 224, may have the option to continue therapy once the adverse events recover to baseline or Grade 1 and the re-introduction of AMG 224 is deemed safe by the investigator, Amgen's medical monitor, and Global Safety Officer. The subject should

restart at a reduced dose (see [Section 6.2.1.4](#)) subsection Dose Adjustments).

- Intolerability of the study treatment
- The dosing is delayed > 3 weeks due to AMG 224-related adverse events
- Disease progression according to IMWG response criteria
- Clinical significant deterioration of health status

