6.4.2 Criteria for Conditional Withholding of AMG 224 due to Potential Hepatotoxicity

For subjects who do not meet the criteria for permanent withholding of AMG 224 outline above and with no underlying liver disease and eligibility criteria requiring normal transaminases and TBIL at baseline or subjects with underlying liver disease and baseline abnormal transaminases, the following rules are recommended for conditional withholding of AMG 224 and other protocol-required therapies:

- Elevation of either AST or ALT according to the following schedule:

Baseline AST or ALT value	AST or ALT elevation
Any	> 8x ULN at any time
Any	> 5x ULN but < 8x ULN for ≥ 2 weeks
Any	> 5x ULN but < 8x ULN and unable to adhere to enhanced monitoring schedule
Any	> 3x ULN with clinical signs or symptoms that is consistent with hepatitis (such as right upper quadrant pain/tenderness, fever, nausea, vomiting, jaundice, rash or eosinophilia (> 5%).

- OR: TBIL > 3x ULN at any time
- OR: ALP > 8x ULN at any time

AMG 224 should be withheld pending investigation into alternative causes of DILI. If investigational product is withheld, the subject should be followed according to recommendations in [Appendix A](#) for possible DILI. Rechallenge may be considered if an alternative cause for impaired liver tests (ALT, AST, ALP) and/or elevated TBIL is discovered and the laboratory abnormalities resolve to normal or baseline.

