Appendix A. Additional Safety Assessment Information

Adverse Event Grading Scale

The CTCAE version 4.0 is available at the following location:

https://ctep.cancer.gov/protocoldevelopment/electronic_applications/ctc.htm

Drug-induced Liver Injury Reporting & Additional Assessments

Reporting

To facilitate appropriate monitoring for signals of DILI, cases of concurrent AST or ALT and TBL and/or INR elevation according to the criteria specified in [Section 6.4](#) require the following:

- The event is to be reported to Amgen as a serious adverse event within 24 hours of discovery or notification of the event (ie, before additional etiologic investigations have been concluded)
- The appropriate eCRF (eg, Event eCRF) that captures information necessary to facilitate the evaluation of treatment-emergent liver abnormalities is to be completed and sent to the Amgen.

Other events of hepatotoxicity and potential DILI are to be reported as serious adverse events if they meet the criteria for a serious adverse event defined in [Section 9.2.1.2](#).

Additional Clinical Assessments and Observation

All subjects in whom investigational product is withheld (either permanently or conditionally) due to potential DILI as specified in [Sections 6.4.2](#) and [6.4.3](#) or who experience AST or ALT elevations $> 3 \times$ ULN are to undergo a period of “close observation” until abnormalities return to normal or to the subject’s baseline levels.

Assessments that are to be performed during this period include:

- Repeat AST, ALT, ALP, bilirubin (total and direct), and INR within 24 hours
- In cases of TBL $> 2 \times$ ULN or INR > 1.5 , retesting of liver tests, BIL (total and direct), and INR is to be performed every 24 hours until laboratory abnormalities improve
- Testing frequency of the above laboratory tests may decrease if the abnormalities stabilize or the investigational product has been discontinued AND the subject is asymptomatic.
- Initiate investigation of alternative causes for elevated AST or ALT and/or elevated TBL:
 - Obtain complete blood count (CBC) with differential to assess for eosinophilia
 - Obtain serum total immunoglobulin IgG, Anti-nuclear antibody (ANA), Anti Smooth Muscle Antibody, and Liver Kidney Microsomal antibody 1 (LKM1) to assess for autoimmune hepatitis

Approved

- Obtain serum acetaminophen (paracetamol) levels
- Obtain a more detailed history of:
 - Prior and/or concurrent diseases or illness

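### The permanent liver stop in 6.4.1 and the Appendix A combined-elevation DILI report have no defined trigger for subjects who enter with AST/ALT at or above ULN, whom inclusion 111 admits

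*Protocol*

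**What the plan says.** **Eligibility (4.1, inclusion 111).** AST and ALT must be below 3x ULN and total bilirubin below 1.5x ULN, the bilirubin limit applying to all "except subjects with Gilbert's syndrome". No bilirubin cap is stated for those subjects. Normal transaminases are not required.

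**Permanent withholding (6.4.1).** The drug is stopped for good "if ALL of the criteria below are met". The first criterion is "Increased AST or ALT from the relevant baseline value as specified below". Its table has a single row: baseline below ULN, elevation above 3x ULN. The second is "TBIL > 2 x ULN or INR > 1.5". The third is that no other cause is immediately apparent.

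**Conditional withholding (6.4.2).** The lead-in describes subjects "with no underlying liver disease and eligibility criteria requiring normal transaminases and TBIL at baseline", or else subjects with underlying liver disease and abnormal baseline transaminases. All four AST/ALT rows of its table are marked as applying to any baseline.

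**Routine hold (6.2.1.5).** Dosing is withheld for "Aspartate aminotransferase (AST) or alanine aminotransferase (ALT) greater than 3x ULN or total bilirubin greater than 1.5x ULN". It may resume on return to grade 1 or better, or to the subject's baseline, if the investigators and medical monitor judge this safe.

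**Reporting (Appendix A).** The automatic 24-hour report as a serious adverse event covers "cases of concurrent AST or ALT and TBL and/or INR elevation according to the criteria specified in" Section 6.4. Other hepatotoxicity is reported as an SAE only if it meets the SAE criteria.

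**The concern.** The 6.4.1 wording implies a threshold for each relevant baseline, yet only one baseline stratum has one. Inclusion 111 admits a second stratum, from ULN to just under 3x ULN. In that stratum the joint condition in 6.4.1 cannot be met as written, whatever the later AST, bilirubin or INR.

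Hepatotoxicity is one of the two toxicities that protocol section 2.3 names as anticipated. If two subjects with the same on-treatment results are stopped and reported differently because one entered with mildly raised enzymes, the permanent stops and expedited DILI reports that reach the dose level review team are not comparable across subjects. The SAP will not recover the difference automatically. Its listing of potential Hy's law cases is built on AST, ALT and bilirubin, so a case defined by INR would appear only in the general coagulation and chemistry outputs.

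**Working it through.** No computed figure is involved, so the check compares the baselines admitted by 111 with each liver rule.

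**Step 1. Coverage of 6.4.1.** The rule is: (baseline < ULN and AST/ALT > 3x ULN) AND (TBIL > 2x ULN or INR > 1.5) AND no other cause. Inclusion 111 admits baselines below 3x ULN. The admitted range without a row is therefore ULN ≤ baseline < 3x ULN.

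**Step 2. Same results, two baselines.** On treatment, both subjects have AST 4x ULN, INR above 1.5, TBIL at or below 2x ULN, no hepatitis symptoms, ALP not above 8x ULN and no other cause.

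| Rule | Baseline < ULN | Baseline 1.5x ULN |
|---|---|---|
| 6.4.1 permanent stop | Met | No row; not met |
| Appendix A automatic 24-hour report | Met through 6.4.1 | No defined trigger |
| 6.4.2 conditional withholding | Superseded by 6.4.1 | Not met: 4x is below the 5x and 8x rows, there are no symptoms, and TBIL is not above 3x |
| AST/ALT and TBIL DLT limbs (6.2.1.6) | Not met | Not met |
| Hy's law case (6.2.1.6) | Not met: TBIL not above 2x | Not met |
| 6.2.1.5 hold (AST/ALT > 3x) | Met | Met; temporary |
| Close observation (Appendix A) | Met | Met |

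The second subject gets a hold that may be lifted on return to baseline, and a report only if the investigator judges the event serious. By the listed limits, the same outcome extends to AST/ALT between 5x and 8x ULN for less than two weeks in a subject who keeps to enhanced monitoring. The general DLT clause depends on CTCAE grades that the protocol does not reproduce, so it is not relied on here.

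**Step 3. A severe case.** Baseline is 1.5x ULN, AST rises to 10x and TBIL to 4x ULN, with no cholestasis and no other cause. The AST limb is met (10 > 8), as are the TBIL limb (4 > 3) and Hy's law (10 ≥ 3 and 4 > 2). Under 6.2.1.5, events meeting DLT criteria at any time lead to permanent discontinuation. The responder exception is closed by the bar on rechallenge after DILI meeting Hy's law. The missing row does not change the stop.

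**Step 4. The 6.4.2 lead-in.** It names two groups: eligibility requiring normal values without liver disease, or liver disease with abnormal transaminases. A subject admitted by 111 with raised enzymes and no liver disease fits neither. Steps 2 and 3 let the table's any-baseline label prevail over the lead-in.

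**Step 5. Gilbert's syndrome.** Inclusion 111 sets no bilirubin ceiling for these subjects, and the 6.2.1.5 hold at TBIL > 1.5x ULN names no exemption. An eligible subject can meet the hold condition before the first dose. This is separate from the 6.4.1 row, which restricts baseline AST/ALT and not bilirubin.

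**Size.** The documents do not say how many subjects enter with AST or ALT at or above ULN. As an unanchored assumption, 5% to 20% of about 60 subjects gives 0.05 × 60 = 3 to 0.20 × 60 = 12. Only a subset of these could reach the combination in Step 2.

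**The case against.** A reader might infer that the liver stopping rules as a whole fail for subjects with raised baseline enzymes. The documents do not support that. The 6.4.2 table, the 6.2.1.5 hold, the AST/ALT, TBIL and Hy's law DLT limbs, the bar on rechallenge after Hy's law DILI, and close observation all apply at any baseline. Step 3 shows a severe case still stopped for good.

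Even the residual case is not unmanaged. Dosing is held, restart needs the medical monitor's agreement, a related delay of more than three weeks ends treatment, and Appendix A requires retesting every 24 hours while INR exceeds 1.5. Reporting also has a fallback: section 9.1.2 gives DILI as an example of a medically important serious event, and SAEs go to the sponsor within 24 hours. Where AST/ALT and bilirubin both pass their separate 6.4.2 limits, one could argue that the Appendix A trigger is met through 6.4.2. All of this stands, and it narrows the point. It does not supply the permanent stop or the automatic report in the INR case, because the combination of raised AST/ALT with raised INR appears only in 6.4.1.

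A reader might also infer that Gilbert's subjects will produce spurious bilirubin DLTs and distort dose decisions. The attribution clauses largely answer this: the DLT definition excludes events clearly due to other causes, the Hy's law definition requires no alternative reason, and 6.4.1 lists Gilbert's as an alternative cause. Nothing shows that such subjects enter near 3x ULN. Only the mismatch with the 6.2.1.5 hold remains.

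Finally, the finding rests on an absent row in a table read from PDF. A lost row cannot be excluded, although the similar 6.4.2 table came through with all four rows.

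**Conclusion.** The contradiction is real but narrower than it first appears. For baseline AST/ALT from ULN to just under 3x ULN, the 6.4.1 permanent stop and the Appendix A combined-elevation report have no defined trigger, and the 6.4.2 lead-in misdescribes eligibility. The main practical consequence is confined to AST/ALT above 3x ULN with INR above 1.5, TBIL at or below 2x ULN and no symptoms. The Gilbert's mismatch is secondary.

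This assumes that the 6.4.1 table is complete as it reads and that neither enzyme satisfies the row. Because the row refers to AST or ALT, a subject with one normal and one raised enzyme at entry might still satisfy it, which would make the affected group smaller. The point deserves correction because it concerns an anticipated toxicity and can be settled by wording alone.

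**What to change.** Check the 6.4.1 table against the approved protocol. If the single row is confirmed, reconcile inclusion 111, the 6.4.1 table, the 6.4.2 lead-in and the Appendix A reporting trigger, so that the permanent-stop and reporting criteria are defined for every baseline AST/ALT value that 111 admits. Reconcile the Gilbert's exemption in 111 with the 6.2.1.5 bilirubin hold. The sponsor sets any thresholds; none is proposed here.

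Two cross-references in the same sections should be checked at the same time. Section 6.4.3 cites 6.2.1.4, which concerns holding enrollment, for the permanent-discontinuation criteria. Appendix A cites 6.4.2 and 6.4.3, but not 6.4.1, for permanent or conditional withholding.

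The cost is protocol wording and possibly a few more DILI reports. No new tests are needed.

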6.4.2 Criteria for Conditional Withholding of AMG 224 due to Potential Hepatotoxicity

For subjects who do not meet the criteria for permanent withholding of AMG 224 outline above and with no underlying liver disease and eligibility criteria requiring normal transaminases and TBIL at baseline or subjects with underlying liver disease and baseline abnormal transaminases, the following rules are recommended for conditional withholding of AMG 224 and other protocol-required therapies:

- Elevation of either AST or ALT according to the following schedule:

Baseline AST or ALT value	AST or ALT elevation
Any	> 8x ULN at any time
Any	> 5x ULN but < 8x ULN for ≥ 2 weeks
Any	> 5x ULN but < 8x ULN and unable to adhere to enhanced monitoring schedule
Any	> 3x ULN with clinical signs or symptoms that is consistent with hepatitis (such as right upper quadrant pain/tenderness, fever, nausea, vomiting, jaundice, rash or eosinophilia (> 5%).

- OR: TBIL > 3x ULN at any time
- OR: ALP > 8x ULN at any time

AMG 224 should be withheld pending investigation into alternative causes of DILI. If investigational product is withheld, the subject should be followed according to recommendations in [Appendix A](#) for possible DILI. Rechallenge may be considered if an alternative cause for impaired liver tests (ALT, AST, ALP) and/or elevated TBIL is discovered and the laboratory abnormalities resolve to normal or baseline.

